APPENDIX 4: MODIFIED RESPONSE EVALUATION CRITERIA IN SOLID TUMORS: RECIST 1.1

General Guidelines

- The same diagnostic method, including use of contrast when applicable, must be used throughout the study to evaluate a lesion.
- All measurements should be taken and recorded in millimeters (mm), using a ruler or calipers.
- Ultrasound is not a suitable modality of disease assessment. If new lesions are identified by ultrasound, confirmation by CT or MRI is required.

Clinical Examination: Clinical lesions will only be considered measurable when they are superficial (e.g., skin nodules and palpable lymph node) and ≥ 10 mm (≥ 1 cm) diameter as assessed using calipers (e.g., skin nodules). In the case of skin lesions, documentation by color photography including a ruler or calipers to estimate the size of the lesion is recommended.

CT and MRI: Contrast enhanced CT with 5 mm contiguous slices is recommended.

Minimum size of a measurable baseline lesion should be twice the slice thickness, with a minimum lesion size of 10 mm when the slice thickness is 5 mm. MRI is acceptable, but when used, the technical specification of the scanning sequences should be optimized for the evaluation of the type and site of disease and lesions must be measured in the same anatomic plane by use of the same imaging examinations. Whenever possible the same scanner should be used.

X-ray: X-ray should not be used for target lesion measurements owing to poor lesion definition. Lesions on chest X-ray may be considered measurable if they are clearly defined and surrounded by aerated lung; however, chest CT is preferred over chest X-ray.

Bone Scans (Bone Scintigraphy)

For subjects without bone disease at baseline: baseline and subsequent bone scans should only be performed as clinically indicated (e.g., presentation of bone pain).

For subjects with bone disease at baseline: For Cycles 1 through 12, a bone scan is required every 8 weeks or as clinically indicated. For Cycles 13 and beyond, a bone scan is required every 12 weeks or as clinically indicated. In addition, in order to assign a response of CR in a subject with bone disease at baseline, a bone scan must be performed within 4 weeks after the first set of images showing CR. If a bone scan is performed and a new lesion(s) is equivocal, then correlative imaging (i.e., X-ray, CT scan, or MRI) is required to demonstrate malignant characteristics of the lesion(s).

Brain Scans

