Note: Stable doses of corticosteroids include subjects not on corticosteroids.

Disease progression (PD): PD is defined by any of the following:

- $\geq 25\%$ increase in sum of the products of perpendicular diameters of enhancing lesions compared with the smallest tumor measurement obtained either at baseline (if no decrease) or best response, on stable or increasing doses of corticosteroids
- significant increase in T2/FLAIR non-enhancing lesion on stable or increasing doses of corticosteroids compared with baseline scan or best response after initiation of therapy not caused by co-morbid events (e.g., radiation therapy, demyelination, ischemic injury, infection, seizures, post-operative changes, or other treatment effects)
- any new lesion; clear clinical deterioration not attributable to other causes apart from the tumor (e.g., seizures, medication adverse effects, complications of therapy, cerebrovascular events, infection) or changes in corticosteroid dose
- failure to return for evaluation as a result of death or deteriorating condition
- clear progression of non-measurable disease

Summary of RANO Response Criteria

Criterion	CR	PR	SD	PD
T1 gadolinium-enhancing disease	None	$\geq 50\%$ decrease	$< 50\%$ decrease but $< 25\%$ increase	$\geq 25\%$ increase ^a
T2/FLAIR	Stable or decrease	Stable or decreasing	Stable or decrease	Increase
New Lesion	None	None	None	Present
Corticosteroids	None	Stable or decreasing dose	Stable or Decreasing dose	NA ^b
Clinical Status	Stable or increase	Stable or increase	Stable or increase	Decrease
Requirement for Response	All	All	All	Any

Abbreviations: CR, complete response; FLAIR, fluid-attenuated inversion recovery; NA, not applicable; PD, progressive disease; PR, partial response; RANO, Response Assessment in Neuro-Oncology; SD, stable disease (Wen, 2010).

^{a.} Progression occurs when this criterion is present.

^{b.} Increase in corticosteroids alone will not be taken into account in determining progression in the absence of persistent clinical deterioration.

CCI

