15.2. PROGRESSION-FREE SURVIVAL

- PFS per appropriate criteria will be analyzed and listed for the ITT population only for the dose expansion phase of the study. PFS is defined as the interval of time (in weeks) from the date of first dose of study drug and the earliest date of disease progression or death, from any cause. For subjects who progressed or died after an extended period without adequate assessment, PFS will be censored at their date of last adequate assessment prior to progression or death even if subsequent information is available regarding progression or death. An adequate assessment is defined as an assessment where the Investigator determined response is CR, PR, or SD. The date of response at that assessment will be used for censoring.
- For subjects who receive subsequent anticancer therapy prior to the date of documented progression or death, PFS will be censored at the last adequate assessment (i.e., last assessment of CR, PR or SD) prior to the initiation of that anticancer therapy.
- For subjects who do not progress or die, PFS will be censored at the date of the last adequate tumor assessment.

PFS censoring rules are defined in Table 4 below.

In dose expansion, PFS will be summarized by cohort and overall. PFS will be analysed using the Kaplan-Meier method. Median PFS, first and third quartiles and associated 95% 2-sided CIs, will be estimated using the Brookmeyer-Crowley method [Brookmeyer, 1982]. PFS at 24 weeks and 56 weeks along with the associated 2-sided 95% CIs, will be provided. Kaplan-Meier PFS curves also will be provided.

Table 4: Date of Event of Censoring for PFS

Situation	Date of Event (PD/Death) or Censoring	Outcome: Event (PD/Death) or Censored
No (or inadequate) baseline tumor assessments and the subject has not died	Date of Study Day 1	Censored
No post-baseline assessments and the subject has not died (if the subject has died follow the rules for death indicted at the bottom of the table)	Date of Study Day 1	Censored
Progression documented between scheduled visits	Date of assessment of progression ¹	Event
No progression (or death) and no new anti-cancer treatment documented	Date of last ‘adequate’ assessment of response ²	Censored
No progression (or death) and new anti-cancer treatment documented	Date of last ‘adequate’ assessment of response ² on or prior to starting anti-cancer therapy	Censored

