New anti-cancer treatment started (prior to documented disease progression or death). ³	Date of last ‘adequate’ assessment of response ² on or prior to starting anti-cancer therapy	Censored
Death before first PD assessment (or Death at baseline or prior to any adequate assessments)	Date of death	Event
Death between adequate assessment visits	Date of death	Event
Death or progression after one missed visit (with 2 week window)	Date of last ‘adequate’ assessment of response ² prior to missed assessments	Censored

¹ The earliest of (i) Date of radiological assessment showing new lesion (if progression is based on new lesion); or (ii) Date of radiological assessment showing unequivocal progression in non-target lesions, or (iii) Date of last radiological assessment of measured lesions (if progression is based on increase in sum of measured lesions)

² An adequate assessment is defined as a radiological assessment where CR, PR, or SD was determined.

³ If PD and subsequent anti-cancer therapy occur on the same day assume the progression was documented first, e.g., outcome is progression and the date is the date of the assessment of progression). If anti-cancer therapy is started prior to any adequate assessments, censoring date should be the date of Study Day 1.

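### SAP Table 4 dates PFS events by radiology only, so RANO clinical progression and caliper-measured progression have no defined date and may be censored

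*SAP*

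**What the plan says.** **SAP 15.2, text.** PFS is analysed by the criteria appropriate to the disease and runs from first dose to the earlier of progression or death. The text states: "An adequate assessment is defined as an assessment where the Investigator determined response is CR, PR, or SD". Protocol 14.4.2 has the same definition, and SAP 15 bases the efficacy summaries on investigator assessments.

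**SAP Table 4, footnote 1.** The progression date is the earliest of three dates: the scan showing a new lesion, the "Date of radiological assessment showing unequivocal progression in non-target lesions", or the last scan of measured lesions when their sum has increased. All three are radiological.

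**SAP Table 4, footnote 2, and the footnote to Table 3 (DOR).** "An adequate assessment is defined as a radiological assessment where CR, PR, or SD was determined".

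**Protocol Appendix 5 (RANO).** Any one listed criterion is enough for progression. The list includes "clear clinical deterioration not attributable to other causes apart from the tumor" and "failure to return for evaluation as a result of death or deteriorating condition".

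**Protocol Appendix 4 (RECIST 1.1) and 8.5.3.** "Clinical lesions will only be considered measurable when they are superficial" and at least 10 mm by calipers. Section 8.5.3 accepts such a lesion as measurable disease for the expansion cohorts.

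**The concern.** The SAP defines one term in two ways, and its dating rule is narrower than the criteria it applies. A RANO progression recorded on clinical grounds, or a RECIST progression recorded from a caliper measurement, is a PFS event under the 15.2 text, yet footnote 1 gives it no date. Whoever programs the endpoint must then decide whether it is an event, and on what day.

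The choice matters because a child who declines before the next scan is likely to be among the fastest to progress. Removing such subjects by censoring is informative and pushes PFS upwards. If the same progression still counts as PD in the best overall response table (SAP 15.1), the two outputs will disagree. Clinical progression arises only under RANO, so the effect falls mainly on Cohort 1 (ATRT).

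**Working it through.** **1. The plan's own figure.** The only design figure is for ORR: at least 3 responses in 20, null 5%, alternative 20% (protocol 14.2.1). Exact binomial: P(X ≥ 3 | 0.05) = 7.55% and P(X ≤ 2 | 0.20) = 20.6%, matching the stated 8% and 21%. This rule uses no PFS date. No sample size or power is stated for PFS.

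**2. Each kind of progression set against Table 4.**

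| Progression | Event under the 15.2 text? | Date in footnote 1? | Row that might capture it |
|---|---|---|---|
| RANO clinical deterioration, no scan | Yes | None | Documented progression (event), or no post-baseline assessments and alive (censored, Day 1) |
| RANO failure to return through deterioration | Yes | None | Progression or death after one missed visit (censored, last adequate assessment) |
| RECIST growth of a caliper lesion | Yes | None; item three needs a scan | Documented progression (event), or censored at the last scan if footnote 1 is read as defining PD |

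A later scan need not fill the gap. Protocol 9.4 continues 8-weekly disease assessment for subjects who stop for reasons other than progression, so a child taken off treatment for clinical progression falls outside it. Appendix 4 also requires a lesion to be followed by the same method throughout.

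**3. A case.** A child with ATRT has RANO clinical progression recorded at week 5 with no post-baseline scan, and then starts another therapy. By the 15.2 text this is an event at week 5. If footnote 1 is taken to define progression, no progression exists; the row for no post-baseline assessments, or the last sentence of footnote 3, then gives censoring at Day 1.

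**4. Size if censored at Day 1.** Assume 20 subjects, 4 of them progression-free at week 24, the other 16 progressing before then, and c of those 16 censored at Day 1 with nobody else censored. The c subjects leave the risk set before any event, so the Kaplan-Meier estimate is 4/(20 − c):

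- c = 0: 4/20 = 20.0%
- c = 3: 4/17 = 23.5%
- c = 4: 4/16 = 25.0%
- c = 5: 4/15 = 26.7%

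**5. Size if censored at the last scan.** Assume exponential PFS with 24-week value S, scans every 8 weeks (protocol Table 11), a share q of progressions that are clinical only, and no death event recovered for those censored. Let p = S^(1/3) be the chance of passing one 8-week interval. Among subjects entering an interval, (1 − q)(1 − p) have an event at the next scan and (1 − q) + qp are at risk there. The Kaplan-Meier factor is therefore p/[1 − q(1 − p)], and the 24-week estimate is S/[1 − q(1 − p)]³. For S = 0.20, p = 0.585; with q = 0.10 this gives 0.20/0.8805 = 22.7%.

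| True 24-week PFS | q = 10% | q = 20% | q = 30% | q = 50% |
|---|---|---|---|---|
| 10% | 11.8% | 14.1% | 16.9% | 25.5% |
| 20% | 22.7% | 25.9% | 29.8% | 40.2% |
| 30% | 33.2% | 36.8% | 41.0% | 51.6% |
| 40% | 43.3% | 47.0% | 51.2% | 61.1% |

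The shift is about 2 to 22 percentage points over this range. A simulation of 100,000 subjects per setting agrees within sampling error. The documents give neither S nor q.

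**The case against.** The strongest reply is that the SAP does not censor these events. PFS is defined by the appropriate criteria, RANO clinical decline is progression under them, and Table 4 makes documented progression an event. On this view footnote 1 supplies a date and does not redefine progression. In the week-5 case progression was documented before the new therapy, so the new-therapy row does not apply; footnote 3 even puts progression first when both fall on one day. This stands. A reader might infer that clinical progression simply falls to censoring under Table 4, but the documents do not support that as a general statement. Censoring needs a literal reading of footnote 1, except for failure to return, where the missed-visit row can censor explicitly.

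Other limits also stand:

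- **DOR.** A reader might infer that DOR events lose their dates too. They do not: Table 3 dates progression by the first disease assessment that shows it, with no radiological limit. Only its adequate-assessment footnote, and hence the censoring dates, is affected.
- **Calipers.** A reader might infer that caliper-followed subjects have no adequate assessment at all. Protocol 8.5.3 and Table 11 call for 8-weekly assessment with CT or MRI, so follow-up by caliper alone is possible but probably uncommon.
- **RECIST.** Appendix 4 keeps symptomatic deterioration separate from objective progression, so the clinical part concerns RANO-assessed tumours only.
- **Deaths.** Table 4 counts death before the first progression assessment as an event, so some of these subjects would re-enter as later events. The calculations ignore this.
- **Precision.** The exact 95% interval for 4/20 is 5.7% to 43.7%, far wider than a shift of 3.5 to 6.7 points.

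These points limit the size. They do not remove the conflict between footnote 2 and the 15.2 text, or supply the missing date. Protocol 14.3.3 requires deviations from its analysis plan to be documented, and SAP 3.2 lists no radiology-only restriction.

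**Conclusion.** The point holds as a conflict and a gap in the PFS rules. Footnote 2 of Table 4 contradicts SAP 15.2 and protocol 14.4.2, and footnote 1 gives no date for RANO clinical progression or caliper-measured RECIST progression. Whether these become events or are censored is left to the programmer. For RANO failure to return, the missed-visit row can explicitly censor what Appendix 5 calls progression.

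Any such censoring would raise PFS estimates, chiefly in Cohort 1. Its size cannot be derived from the documents: the 20% baseline, the 3 to 5 subjects, and the 10% to 50% shares of clinical-only progression are all assumptions. PFS is a secondary endpoint with no hypothesis test, and the primary ORR and its 3-of-20 rule are unaffected. The SAP should be corrected, but this does not threaten the trial's main conclusion.

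**What to change.** - **Table 4 footnote 2 and the Table 3 footnote:** replace the radiological wording with the 15.2 definition, namely an investigator assessment of CR, PR or SD by RECIST 1.1 or RANO as applicable.
- **Table 4 footnote 1:** add the date of the investigator assessment documenting RANO progression by clinical deterioration, and the date of the caliper measurement showing RECIST progression.
- **RANO failure to return because of deterioration:** state which date is used, and exempt this case from the row that censors after one missed visit. Without the exemption that row could override the new dates.
- **Optional:** keep radiology-only PFS as a sensitivity analysis.

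The cost is SAP wording and minor programming, after checking that the eCRF (not among the documents) captures the date of clinical progression. The drawbacks are that clinical dates are more subjective than scan dates and that PFS may come out slightly less favourable.

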15.3. OVERALL SURVIVAL

OS will be analyzed and listed for the ITT population. OS is defined as the interval of time (in weeks) between the date of first dose of study drug and the date of death from any cause. Subjects who have not died will be censored at the date of last contact which may be identified from a visit date, study assessment (physical examination, vital signs, performance status, ECG, study drug record, radiological evaluation), AE, medication, or disposition information.

In dose expansion, OS will be summarized by cohort and overall.

OS will be analysed using the Kaplan-Meier method. Median OS, first and third quartiles and associated 95% 2-sided CIs, will be estimated using the Brookmeyer-Crowley method [Brookmeyer, 1982]. OS at 24 weeks and 56 weeks along with the associated 2-sided 95% CIs, will be provided. Kaplan-Meier OS curves also will be provided.

Listings of efficacy response data and overall survival will be provided.

16. PERFORMANCE STATUS ANALYSIS

Karnofsky/Lansky performance status score will be analyzed and listed for the ITT population. Performance status will be summarized at baseline and by best and worst post-baseline value, by dose level and cohort and overall. A summary of shift from baseline to the best post-baseline value and to the worst post-baseline value during the study, by study part and overall will be provided. Best and worst post-baseline values will be flagged in the listing.

17. SAFETY OUTCOMES

Safety summaries will be based on the Safety population (except for summaries on DLTs which will be based on the DLT population).

17.1. ADVERSE EVENTS

Verbatim AEs terms will be coded using the Medical Dictionary for Regulatory Activities (MedDRA) version in effect at the time of the analysis. Summary tables will be based on treatment emergent adverse events (TEAEs) which are defined as AEs that started or worsened

in severity on or after the day of the first dose of study drug through 30 days after the end of study drug. Missing or partially missing start and end dates for AEs and SAEs will be handled according to the conventions described in Appendix A. For cases in which it is not possible to ascertain treatment-emergence, the event will be classified as treatment-emergent. All AEs, treatment emergent or otherwise, will be presented in subject data listings.

Each summary table will include the incidence (number and percentage) of subjects reporting any TEAE, as well as, by SOC and PT. A subject will be counted once within an SOC, even if the subject experienced more than one TEAE within a specific SOC (likewise for PT).

Investigator assessed severity grade will be based on the National Cancer Institute CTCAE, version 4.03. For summary purposes, TEAEs with a missing severity will be classified as missing. A subject will be counted once at the worst severity grade within a SOC and/or PT.

Investigator assessed causality to study drug will be categorized as “not related,” “unlikely related,” “possibly related,” or “related” to study drug. For summary purposes, treatment-related TEAEs will include events with relationship to study drug classified as “possibly related” or “related”. A TEAE with a missing causality will be classified as “possibly related” to study drug. A subject will be counted once at the strongest causality within a SOC and/or PT.

TEAEs of special interest are defined in Section 10.4 of the protocol. In consultation with study clinicians, this subset of TEAEs will be identified using MedDRA terms.

An overview summary table of subjects with TEAEs will be provided by study part and overall and will include the number of subjects with any TEAE, any TEAE Grade 3 or 4, any TEAE DLT (as defined in the protocol Section 6.3), any treatment-related TEAE, any treatment-related TEAE Grade 3 or 4, any TEAE leading to dose reduction, any TEAE leading to study drug interruption, any TEAE leading to discontinuation of study drug, any TEAE leading to study discontinuation, any serious TEAE (TESAE), any treatment-related TESAE, any protocol defined TEAE of special interest. In accordance with the TEAE table presentation described above, AEs will be summarized by study part and overall as follows:

- TEAEs
- TEAEs with $\geq 10\%$ incidence overall based on PT
- TEAEs of grade 3 or 4
- Treatment-related TEAEs
- Treatment-related TEAEs of grade 3 or 4
- TEAEs leading to dose interruption
- TEAEs leading to dose reduction

- TEAEs leading to discontinuation of study drug
- TEAEs leading to discontinuation from study
- Treatment-emergent serious adverse events (SAEs)
- Treatment-related treatment emergent SAEs
- TEAEs of special interest
- DLTs

Additionally, separate listings of DLTs, SAEs, , TEAEs leading to discontinuation of study drug and TEAEs leading to dose modifications (interruption and dose reduction). A listing of TEAEs of special interest will be also provided.

Adverse events with CTCAE Grade 5 or outcome of death are excluded from AE summary tables and summarized under death related tables.

Deaths

Deaths will be summarized and listed as follows:

- Summary and listing of subjects who died during and till 30 days after last dose of study drug
- Summary and listing of subjects who died during and till 30 days after last dose of study drug with treatment-related TEAEs
- Summary and listing of subjects who died after 30 days after the last dose of study drug with treatment-related AEs

The summary and listing will include the reason for death:

- Any AE (by MedDRA preferred Term)
- Any treatment related TEAE
- Progression
- Tumor progression
- Disease under Study

- Unknown/Other causes

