9.4 Survival Follow-Up

Subjects who discontinue study treatment for reasons other than disease progression will continue to have disease assessments, when possible, every 8 weeks until disease progression or death. In addition, subjects who permanently discontinue study treatment will be followed (by phone, email, or clinic visit) for survival every 16 weeks until death, withdrawal of consent, or they are lost to follow-up. AESI and subsequent anti-cancer therapy information will be collected throughout the survival follow up.

Survival follow-up will continue for 2 years for each subject or until 80% of subjects enrolled have died.

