10.9 Timeframe for Reporting AEs and SAEs

AEs: Adverse events will be collected from the time the first dose of study treatment is administered until the earlier of either 30 days after the discontinuation of study treatment or until the initiation of subsequent anticancer therapy.

SAEs: SAEs will be collected over the same time period as stated above for AEs. In addition, any SAE assessed **as related** to study participation (e.g., protocol-mandated procedures, invasive tests, or change in existing therapy), study treatment must be recorded from the time a subject provides consent to participate in the study up to and including any follow-up contact. All SAEs will be reported to the Sponsor within 24 hours.

After discontinuation of study treatment: The Investigator will monitor all ongoing AEs/SAEs until resolution or stabilization of the event or until the subject is lost to follow-up or has withdrawn consent. Up until 30 days after the last dose of study treatment or until the initiation of subsequent anticancer therapy, whichever is earlier, the Investigator will report any AE that they consider to be possibly related to study treatment. Note that any incidence of secondary lymphoma, even if occurring more than 30 days after the last dose of study drug, will be reported to the Sponsor as in Section 10.4.

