14.5.3 Adverse Events

Treatment-emergent adverse events (TEAEs) are defined by applying treatment-emergent signs and symptoms (TESSs) philosophy. AEs will be regarded as TEAEs if one of the following conditions is met:

- Emerge after the time of the administration of the first dose, having been absent prior to the first dose.
- Re-emerge, having been present but stopped prior to the time of the administration of the first dose.
- Worsen in severity after the time of first dose administration relative to the pre-treatment state, when the AE is continuous.

An AE with partial or completely missing start date and/or time will always be assumed as TEAE, unless it can be determined to be “prior to administration” from the incomplete start date/time or resolution date/time (e.g., month, year is before first administration date, or resolution date is before date of first administration).

Only TEAEs will be summarized. Summaries of TEAEs will consist of the number and percentage of subjects reporting the AE by SOC and by PT. TEAEs which occur more than once for a subject will be counted only once in the subject frequencies. TEAEs with different CTCAE grades for a subject will be counted at the worst (highest) grade for the same SOC (likewise for PT). TEAEs with different drug relationship for a subject will be counted at strongest relationship for the same SOC (likewise for PT). TEAEs with missing relationship to study treatment will be counted as “related”. TEAEs with missing CTCAE grade will be counted as Grade 3 (“severe”).

Summaries of TEAEs by study cohort and overall will be produced to present the number and percentage of subjects with:

- Any TEAE
- Any treatment-related TEAE
- Any TEAE with CTCAE Grade 3 or higher
- Any TEAE leading to study treatment discontinuation
- Any Serious TEAEs
- Any TEAE of special interest

Listings will be provided for the following:

- AEs
- TEAEs leading to study treatment discontinuation
- Serious TEAEs
- Fatal TEAEs
- TEAEs of special interest

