APPENDIX 1. PARTIAL DATES CONVENTIONS

ALGORITHM FOR TREATMENT EMERGENCE OF ADVERSE EVENTS:

START DATE	STOP DATE	ACTION
Known	Known/Partial /Missing	If start date < study drug start date, then not TEAE If start date >= study drug start date and < (end of treatment + 30 days) or start date of new anti-cancer therapy, whichever is sooner, then TEAE If start date > (end of treatment + 30 days) start date of new anti-cancer therapy, whichever is sooner, then not TEAE
Partial, but known components show that it cannot be on or after study drug start date	Known/Partial /Missing	Not TEAE
Partial, could be on or after study drug start date	Known	If stop date < study drug start date, then not TEAE If stop date >= study drug start date, then TEAE
	Partial	Impute stop date as latest possible date (i.e. last day of month if day unknown or 31st December if day and month are unknown), then: If stop date < study drug start date, then not TEAE If stop date >= study drug start date, then TEAE
	Missing	Assumed TEAE
Missing	Known	If stop date < study drug start date, then not TEAE If stop date >= study drug start date, then TEAE
	Partial	Impute stop date as latest possible date (i.e. last day of month if day unknown or 31st December if day and month are unknown), then: If stop date < study drug start date, then not TEAE If stop date >= study drug start date, then TEAE
	Missing	Assumed TEAE

ALGORITHM FOR PRIOR / CONCOMITANT MEDICATIONS:

START DATE	STOP DATE	ACTION
Known	Known	
If stop date < study drug start date, assign as prior
 
If stop date >= study drug start date and start date <= end of treatment + 30 days, assign as concomitant
 
If stop date >= study drug start date and start date > 30 days after the end of treatment, assign as post-treatment

	Partial	
Impute stop date as latest possible date (i.e. last day of month if day unknown or 31st December if day and month are unknown), then:
 
If stop date < study drug start date, assign as prior
 
If stop date >= study drug start date and start date <= end of treatment + 30 days, assign as concomitant
 
If stop date >= study drug start date and start date > 30 days after the end of treatment, assign as post-treatment

	Missing	
If stop date is missing could never be assumed a prior medication
 
If start date <= end of treatment + 30 days, assign as concomitant
 
If start date > 30 days after the end of treatment, assign as post-treatment

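### The SAP's special-interest table and listing stop 30 days after study drug, so secondary malignancies that the protocol collects later reach neither

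*SAP*

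**What the plan says.** **Collection.** Protocol 9.4 states that "AESI and subsequent anti-cancer therapy information will be collected throughout the survival follow up", and footnote y of the schedule of assessments (Table 11) says the same. Survival follow-up runs for 2 years per subject or until 80% of those enrolled have died. Protocol 10.9 ends ordinary AE collection at 30 days after treatment or at subsequent anticancer therapy, whichever is earlier, but makes an exception: "any incidence of secondary lymphoma, even if occurring more than 30 days after the last dose of study drug, will be reported" to the sponsor.

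**Protocol analysis.** Protocol 14.5.3 defines a TEAE by when it starts relative to the first dose ("Emerge after the time of the administration of the first dose, having been absent prior to the first dose" is the first of three conditions) and sets no upper limit. It restricts summaries to TEAEs and words its special-interest row and listing as TEAEs.

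**SAP analysis.** SAP 17.1 keeps the TEAE wording and adds an end date, "in severity on or after the day of the first dose of study drug through 30 days after the end of study drug". For special-interest events it says: "In consultation with study clinicians, this subset of TEAEs will be identified using MedDRA terms". The overview row and the table are limited to TEAEs, and so is the listing: "A listing of TEAEs of special interest will be also provided". The rule in SAP Appendix 1 for a known start date is "If start date > (end of treatment + 30 days) start date of new anti-cancer therapy, whichever is sooner, then not TEAE". SAP 3.2, which lists changes from the protocol's analyses, mentions neither limit.

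**The concern.** The AESIs are T-cell lymphoblastic lymphoma/T-ALL, MDS, AML and other myeloid malignancies such as MPN. They are the one class of adverse event for which the protocol extends collection past the ordinary AE window. The SAP then applies that ordinary window to every special-interest output, so the extra collection has no matching analysis.

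A report in a pediatric patient led to the revised starting doses in Protocol 5.3, and Protocol 6.5.3 adds limits because of AESI risk. Protocol 1.6.5 regards the T-cell risk as concentrated largely in children. Anyone reading the clinical study report for this risk will turn first to the AESI table and listing, and would not learn from them of a case that began 31 days after the last dose.

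The gap is not confined to subjects who have moved on to other treatment. Under Protocol 6.5.3, subjects with stable disease stop drug after one year, and responders may stop one year after first response. Both stay on study until progression, possibly with no other therapy in between.

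**Working it through.** **1. Where a late case would appear.** Take an AESI with a known onset more than 30 days after final dose, and follow it through the outputs in SAP 17.1.

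| Late case | AESI row, table, listing | Other AE tables | SAE listing | All-AE listing | Death summary |
|---|---|---|---|---|---|
| Non-fatal, not serious | no | no | no | yes | no |
| Non-fatal, serious | no | no | yes | yes | no |
| Fatal, treatment-related | no | no | yes | yes | yes |
| Fatal, judged unrelated | no | no | yes | yes | no |

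The first two columns follow from the TEAE restriction. The SAE listing is not worded as TEAE-only, and all AEs are listed whether or not they are treatment-emergent. Fatal events are moved out of the AE tables to the death tables, and beyond 30 days the death tables cover only subjects with treatment-related AEs. A subject in the last row could enter that summary through a different, related AE, but the AESI itself would not be the reason. The death would also still count as an event for overall survival.

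**2. How much follow-up lies inside the window.** The plan states no figure here, so there is none to reproduce.

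- Window after last dose: 30 days = 30/7 = 4.29 weeks (SAP 17.1).
- Follow-up: 2 years from first dose = 104 weeks (Protocol 3.5.1).
- Weeks on drug, W: 8, 16 and 52. These are assumptions.
- Share covered = (W + 4.29)/104.

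| W | Calculation | Covered | Outside |
|---|---|---|---|
| 8 | 12.29/104 | 12% | 88% |
| 16 | 20.29/104 | 20% | 80% |
| 52 | 56.29/104 | 54% | 46% |

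This supposes a subject alive and followed to week 104, with no new therapy. New therapy within 30 days of the last dose would lower the covered share. Death or an earlier end of follow-up would shorten the time outside the window.

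**3. What one case would do.** Protocol 1.6.5 gives 90 pediatric subjects treated by 24 May 2019, and Protocol 1.4.2 gives one pediatric AESI. Suppose, purely as illustration, that a second case arose late in those 90 subjects.

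- Late case left out: 1/90 = 1.1%, exact 95% CI 0.03% to 6.0%.
- Late case counted: 2/90 = 2.2%, exact 95% CI 0.3% to 7.8%.

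With counts this small, one omitted case halves the displayed rate, although the intervals overlap widely.

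**4. Consistency within the SAP.** The new-therapy cut-off is in Appendix 1 but not in the text of 17.1. Appendix 1 applies an upper limit only when the start date is known, so a late AESI with a partial or missing start date can be classed as a TEAE while the same event with a full date is not. When no new therapy intervenes, an onset exactly 30 days after the end of treatment falls in neither class.

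**The case against.** Several points on the other side stand.

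- **The TEAE restriction came from the protocol.** Protocol 14.5.3 already words its AESI outputs as TEAEs, and the SAP's end date matches the ordinary AE collection window in Protocol 10.9. A reader might infer that the protocol had decided to count late AESIs and that the SAP overrode it. The documents do not go that far: 14.5.3 simply gives no end date. What remains is that the SAP adds a limit, that this limit excludes events the protocol collects on purpose, and that SAP 3.2 does not record it, although Protocol 14.3.3 asks for deviations and additions to be documented.
- **Late cases are not hidden.** A reader might infer that they go unreported or are counted nowhere. The table above shows otherwise.
- **Safety oversight does not depend on this table.** AESIs go to the sponsor within 24 hours (Protocol 10.11), the safety committees review all of them, related or not (10.4.3), and a new T-ALL case suspends enrollment (3.4.1). The issue concerns presentation in the study report.
- **The window can be wider than it looks.** For a subject who stops and is later rechallenged, the off-drug interval falls inside it if the end of study drug means the final dose.
- **Late ascertainment is weaker.** Survival contact is every 16 weeks by phone, email or visit, and later therapy can confound a case. That supports a supplementary output and argues against replacing the main one.

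The text of Protocol 10.4.1 and 10.4.2 was not available for this check. The SAP's restriction to TEAEs does not depend on it.

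**Conclusion.** The point holds as a gap in reporting. Under SAP 17.1 and Appendix 1, a secondary malignancy with a known onset after the window enters no special-interest table or listing, even though the protocol collects it. Late non-fatal cases, and late fatal cases judged unrelated, are also counted in no AE or death summary table.

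The size of any understatement is unknown. A reader might take the 46% to 88% of follow-up outside the window as the share of cases that would be missed. The documents do not support that: share of time is not share of events, the treatment durations are assumed, and many subjects will not be followed to week 104. Protocol 1.4.2 reports that 28% of subjects in this study had died on treatment or within 30 days of the last dose. If no late case occurs, nothing is understated. If one does, the AESI table will be wrong for the use most readers make of it.

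A reader might also infer that the any-time rate must become the headline incidence. That is a preference, and nothing in the documents requires it.

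**What to change.** In SAP 17.1, add a supplementary count and listing of all AESIs from first dose to last contact, whether or not they qualify as TEAEs, and including fatal cases. For each case show time from first dose, time from last dose and any anticancer therapy in between. Place this beside the TEAE-window table and keep that table. Record the 30-day and new-therapy limits in SAP 3.2. In the same edit, bring the text of 17.1 and Appendix 1 into agreement on the new-therapy cut-off, on onset at exactly 30 days, and on the upper limit for incomplete start dates.

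The cost is SAP wording, one short table and one listing, from data that Protocol 9.4 already collects. The drawback is that late cases may be confounded by later therapy and are ascertained less intensively than on-treatment events. A note on the listing should say so.
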